#### **7.4.2.4 SF-12**

The Medical Outcomes Study 12-Item Short Form Survey (SF-12) is a questionnaire that measures overall health related quality of life using 12 questions, assessed at Randomization, 6, 12, 18, and 24 months. Summation of standardized questions' scores are used to calculate the PCS and MCS Composite Scores. Scores and change from baseline will be analyzed at each time point and overall in the same manner as the BFI scores. To distinguish clinically meaningful differences from statistically significant differences, the minimum clinically important difference (MCID) will be calculated using a distribution-based approach as 0.5 baseline score standard deviation pooled over treatment groups for each domain. Equivalence will be demonstrated when the entire 95% confidence interval for the adjusted mean difference or change is within the range from  $-MCID$  to  $+MCID$ .

Similar to BFI, SF-12 compliance and completion rates will be calculated at each visit.

#### **7.4.2.5 Expanded Prostate Cancer Index Composite (EPIC)**

The EPIC Hormonal Assessment is a questionnaire used to measure quality of life issues in patients with prostate cancer. There are a total of 11 questions assessed at Randomization, 6, 12, 18 and 24 months related to hormonal function such as hot flashes, breast tenderness, depression, lack of energy, weight fluctuation, etc. The answers range from "more than once a day" to "rarely or never" and "no problem" to "big problem."

The EPIC Sexual Assessment is a questionnaire used to measure quality of life issues in patients with prostate cancer. There are a total of 13 questions assessed at Randomization, 6, 12, 18 and 24 months related to sexual function such as level of sexual desire, ability to have an erection, ability to reach orgasm, quality and frequency of erections, frequency of sexual intercourse, etc. The answers range from "very poor" to "very good," "never" to "daily," and "no problem" to "big problem."

The EPIC Urinary Assessment is a questionnaire used to measure quality of life issues in patients with prostate cancer. There are a total of 12 questions assessed at Randomization, 6, 12, 18 and 24 months related to urinary function such as leaking urine, blood in urine, pain or burning with urination, urinary control and frequency, etc. The answers range from "more than once a day" to "rarely or never" and "no problem" to "big problem."

Total composite and each domain score (hormonal, sexual, and urinary) and their corresponding change from baseline assessments will be analyzed by time point and overall in the same manner as the BFI scores.

If  $>20\%$  of the items that comprise a domain summary score or subscale score are missing a response, the corresponding domain summary or subscale score can not be calculated).

To distinguish clinically meaningful differences from statistically significant differences, the minimum clinically important difference (MCID) will be calculated using a distribution-based approach as 0.5 baseline score standard deviation pooled over treatment groups for each domain score and the total composite score. Equivalence will be demonstrated when the

entire 95% confidence interval for the adjusted mean difference or change is within the range from -MCID to + MCID.

Similar to BFI, EPIC compliance and completion rates will be calculated at each visit for each of the EPIC assessments.

#### **7.4.2.6 Memorial Anxiety Scale for Prostate Cancer**

The Memorial Anxiety Scale for Prostate Cancer (MAX-PC) is a questionnaire used to assess patients' feelings about prostate cancer and PSA tests. There are a total of 18 questions assessed at Randomization, 6, 12, 18 and 24 months related to understanding how patients cope with aspects of their treatment and medical tests frequently involved in their care; questions such as strong feelings about prostate cancer, scared of PSA tests, trouble sleeping due to thoughts of prostate cancer, unable to plan for the future due to prostate cancer, fear of cancer getting worse, etc. The answers range from "not at all" to "often" and "strongly disagree" to "strongly agree."

When there are missing data, if 66% or more questions within scale are answered then a score will be calculated for that scale. Otherwise the patient score for that scale will be missing. For single-item measures, a missing score will not be imputed.

Total composite scores and change from baseline will be analyzed by time point and overall in the same manner as the BFI scores. Composite scores for all licensed instruments will be calculated per the licensing agreements.

Data listings including individual scores, subscale scores and total scores will be provided by treatment group and visit for all patient reported outcomes.

To distinguish clinically meaningful differences from statistically significant differences, the minimum clinically important difference (MCID) will be calculated using a distribution-based approach as 0.5 baseline score standard deviation pooled over treatment groups for each domain score and the total composite score. Equivalence will be demonstrated when the entire 95% confidence interval for the adjusted mean difference or change is within the range from -MCID to + MCID.

Similar to BFI, MAX-PC compliance and completion rates will be calculated at each visit for each of the EPIC assessments.

#### **7.4.2.3 Cancer Positive Cores**

[figure not shown]
Percent of cancer positive cores, assessed using the number of systemically-sampled prostate regions and any targeted regions with at least one positive core (see Section 6.4 for details), will be analyzed at Screening, 12, and 24 months.

Analyses of treatment group differences for the change from baseline composite score will be analyzed with a Mixed Model Repeated Measures (MMRM) model using subject and site as a random factors. For the variance- covariance matrix, compound symmetry (CS), autoregressive (AR1) and unstructured (UN) will be assessed and the best fit will be chosen based on Akaike Information Criteria (AIC) or AICC (correction for finite sample sizes). Degrees of freedom will be approximated using the Kenward-Roger method. Fixed effects will include treatment group, the stratification factors [prostate cancer risk (low/intermediate) and type of biopsy performed (mpMRI targeted/non- mpMRI targeted)], time, time-by-treatment interaction and baseline composite score. Estimates will include 95% confidence

intervals of least square means (LS Means) for each treatment group by nominal time point and overall. P-values will be adjusted using the bonferroni-holm method to adjust for multiplicity. Additionally, assessments of treatment group differences will be made at 3, 6, 12, and 24 months, as well as for the overall model.

**7.4.3**

**CCI**

## 7.5 Analysis of Safety

The following summary tables and listings will be displayed for the SAF.

### 7.5.1 Adverse Events

All AEs will be collected and the severity of the AEs will be evaluated by the investigator based on Version 4.03 of the NCI-CTCAE criteria, updating to the latest version per sponsor decision. All AEs will be coded using the Version 23.0 of the Medical Dictionary for Regulatory Activities (MedDRA) to preferred term, high-level term and system organ class, up versioning every two years per sponsor decision.

Adverse events occurring before randomization will be recorded as medical history events. To maintain naming consistency with subjects on Active Surveillance (AS), Treatment-Emergent Adverse Events (TEAEs) for subjects on Enzalutamide will be reported as Adverse Events (AEs).

An overall summary table will be included that has the following information by treatment group and overall by analysis phase (Treatment, 1-Year Follow-Up and Continued Follow-Up):

- Number and percentage of subjects with AEs
- Number and percentage of subjects with causally drug-related AEs
- Number and percentage of subjects with serious AEs
- Number and percentage of subjects with serious drug-related AEs
- Number and percentage of subjects with AEs leading to permanent discontinuation of study drug,
- Number and percentage of subjects with drug-related AEs leading to permanent discontinuation of study drug
- Number of deaths.

Furthermore, the number of events and number (%) of subjects with AEs, drug-related AEs, serious AEs, drug-related serious AEs, AEs leading to permanent discontinuation of study drug, drug-related AEs leading to permanent discontinuation of study drug, and common AEs occurring in at least 3.5% of any treatment group will be summarized by MedDRA system organ class and preferred term by treatment group and overall. Additional summary tables will be provided for AEs by relationship to study treatment and by CTCAE maximum severity grade. For subjects with missing relationship, the most conservative (related) will be assumed for table summaries.

If a subject reports the same event multiple times, the event will only be displayed once in the summary tables at the highest grade and relationship to study drug.

Version 4.03 of the NCI-CTCAE criteria, updating to the latest version per sponsor decision, will be used to classify laboratory values by toxicity grade.

Listings of AEs, SAEs, Deaths and AEs leading to study drug discontinuation will be displayed by treatment group and site.

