**Table 2 Schedule of Assessments**

Study Visit Name	Screening	Randomization	3m	6m	9m	12m	15m	18m	21m	24m	>24m, q6m 	Unscheduled 
Study Day	-28 to -7	1	85	176	267	358	455	545	635	730	>730	n/a
Week	-4 to -1	1	13	26	39	52	65	78	91	104	>104	n/a
Window (days)			± 7	± 7	± 7	± 7	+7	+7	+7	+7	± 7	n/a
Informed Consent	X											
Medical History 	X		X 									
Inclusion/Exclusion Criteria	X		X									
Randomization		X										
Vital Signs	X		X	X	X	X	X	X	X	X	X	X
Physical Examination, Weight 	X			X	X	X	X	X	X	X	X	X
12-Lead ECG	X 											
MUGA/Echocardiogram 	X 											
Clinical Labs 	X		X	X	X	X	X	X	X	X	X	X
Serum hormone levels 		X			X				X			X
Serum PSA 	X		X	X	X	X	X	X	X	X	X	X 
Digital Rectal Examination	X			X		X		X		X		X 
Transrectal ultrasound-guided prostate biopsy(12 core) 	X 				X				X			X 
BFI 		X	X	X		X		X		X		
SF-12 		X		X	X		X		X		X	
EPIC 		X		X	X		X		X		X	
MAX-PC 		X		X	X		X		X		X	
Adverse Events 	X		X	X	X	X	X	X	X	X	X	X
Concomitant Medications	X		X	X	X	X	X	X	X	X	X	X
Therapies and Outcomes Review	X		X	X	X	X	X	X	X	X	X	X
Study Drug Dispensing 	X		X	X	X	X						
Blood Sample for Potential Future Analysis(optional) 	X		X	X	X	X	X	X	X	X	X	X

1. Subjects will be followed every 6 months until the last subject (study-wide) has completed the 24m Visit.
2. Unscheduled visits may be performed at any time during the study whenever necessary to assess for or follow-up on adverse events (AEs), at the subject's request or if deemed necessary by the investigator.
3. Medical history will include capturing information about any first degree relatives with prostate cancer. Any updates to the subject's medical history will be recorded at the Randomization Visit (Study Day 1) prior to randomization.
4. A complete physical examination will be completed at the Screening Visit. For all visits after the Randomization visit, only a brief physical examination is required.
5. This procedure (if required) must be done within 28 days prior to randomization.
6. A multi-gated acquisition (MUGA) scan or echocardiogram is only required if the subject has a history of anthracycline or anthracenedione (mitoxantrone) treatment.

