**CCI**

#### **3.2 Study Design**

This is a multicenter, randomized, open label exploratory study, conducted in the US and Canada, evaluating the efficacy and safety of enzalutamide for extension of time to prostate cancer progression (pathological or therapeutic) in subjects with clinically localized, histologically proven prostate cancer that is categorized as low risk or intermediate risk and who are under AS. A total of 222 subjects from approximately 50 centers will be enrolled. Subjects are eligible if they were diagnosed within 6 months of screening and have been on AS. A minimum of ten cores from transrectal ultrasound-guided prostate biopsy (mpMRI targeted versus non-mpMRI targeted) are required; confirmatory biopsy before entering the study is not required and is done at the discretion of the investigator.

Low risk is defined as T1c-T2a, PSA $<$ 10, N0, M0 (or presumed N0, M0 if computerized tomography [CT]/bone scan not done due to low risk of metastases), GS  $\leq$  6, ECOG status  $\leq$  2 and estimated life expectancy  $>$  5 years. Intermediate risk is defined as T2b-T2c, PSA $<$ 20, N0, M0 (or presumed N0, M0 if CT/bone scan not done), GS  $\leq$  7 (3+4 pattern only), ECOG status  $\leq$  2 and estimated life expectancy  $>$  5 years.

Prostate cancer progression is defined as either therapeutic progression or pathological progression. Therapeutic progression is defined as the earliest occurrence of primary therapy for prostate cancer (prostatectomy / radiation / focal therapy / systemic therapy). Pathological progression is defined as increase in primary or secondary Gleason pattern by  $>$  1 or higher

proportion of cancer positive cores (>15% increase). Subjects will be stratified by low versus intermediate risk and type of biopsy performed (mpMRI targeted versus non-mpMRI targeted).

Subjects will be randomized (1:1) either to receive treatment with enzalutamide (160 mg), administered as four 40 mg capsules, by mouth, once daily or to AS during the one year study treatment period. Following the one year treatment period, all subjects will be followed for one additional year. Subjects will be followed up every 3 months for these 2 years, after which follow-up will either be every 6 months or unscheduled until the last subject finished their 2 year follow-up. Serum PSA will be measured at baseline and every 3 months during subsequent follow-up visits.

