## 6.4 Other Variables

To clearly state, the following variables are defined:

- Month = 30.4375 days. Year = 365.25 days.
- $BMI(kg/m^2) = Weight(kg) / Height(m^2)$
- Age at randomization=  $\text{floor}((\text{intck}(\text{'month'}, \text{birth date}, \text{randomization date}) - (\text{day}(\text{randomization date}) < \text{day}(\text{birth date}))) / 12)$
- Time since initial/histological diagnosis (years) =  $[(\text{date informed consent signed} - \text{date of initial/histological diagnosis}) + 1] / 365.25$ .
- Time since initial diagnosis to Randomization (years) =  $[(\text{date of Randomization} - \text{date of initial diagnosis}) + 1] / 365.25$ .
- The duration of treatment was calculated as the (last dose date – first dose date) + 1.
- Number of pills taken from one visit to the next = number of pills dispensed – number of pills returned.
- Study drug compliance at each visit is calculated as =  $[(\text{number of pills dispensed} - \text{number of pills returned}) / (4 * \text{number of days in the visit period})] * 100$ .
- Baseline results are defined as the last assessment prior to first dose of study drug, for subjects randomized to once daily enzalutamide. For subjects randomized to active surveillance, baseline is defined as the last assessment prior to or on the date of randomization.
- Treatment Emergent Adverse Events (TEAEs) are any AEs occurring on or after date of first study drug dose date (or randomization for AS) until 30 days post-treatment end date (or 1-year plus 30 days for AS).
- Treatment Phase is defined as date of first study drug dose (or randomization for AS) until either 30 days post treatment end date or (if earlier) study discontinuation date.
- 1-Year Follow-Up Phase is defined as 31 days post treatment end date until either completing 1-Year Follow-Up or (if earlier) study discontinuation date.
- Continued Follow-Up Phase is defined as the day after completing 1-Year Follow-Up phase until study discontinuation date.

Study Day is defined using the following step-wise function:

- If date of interest is on or following randomization, Study Day = Date of Interest – Randomization Date + 1;
- Else, Study Day = Date of Interest – Randomization Date.

Change from baseline is the difference between the result on a post baseline visit and baseline assessment.

Rise in serum PSA is defined as  $PSA \geq 25\% \text{ of baseline or } \geq 25\% \text{ above nadir or } \text{absolute increase} > 2\text{ng/mL}$ .

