## 7 STATISTICAL METHODOLOGY

### 7.1 General Considerations

In general, descriptive statistics are defined for continuous variables as number of subjects (n), mean, standard deviation, minimum, median and maximum, and as frequency and percentage for categorical variables.

In summary and analysis tables of continuous variables, the minimum and maximum statistics will be presented to the same number of decimal places as the original data. The mean, median, quartile, and 2-sided 95% confidence interval (CI) will be presented to 1 more decimal place than the original data. The standard deviation and standard error will be presented to 2 more decimal places than the original data.

In summary tables of categorical variables, the number of non-missing observations and percentages will be presented. Unless specified otherwise, percentages by categories will be based on the number of subjects with no missing data. For categorical variables with missing values, an additional level of the variable will be added to the summary as “Missing” and the frequency will be displayed but no percentage.

Efficacy analysis will be conducted on the FAS and PPS. The primary analysis set for efficacy analyses will be the FAS. The PPS will be used to assess the robustness of the results from the statistical tests based on the FAS. Summaries based on FAS and PPS will be presented by planned treatment group, unless specifically stated otherwise. Safety analysis and other summaries based on SAF will be presented by actual treatment received.

Unless otherwise specified, all statistical testing will be conducted using two-sided tests with a significance level of 0.05.

All statistical analyses will be performed using SAS® v9.3 or higher. Specifications for table, figures, and data listing formats can be found in the TLF specifications for this study.

For the definition of subgroups of interest please refer to section 7.8.

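### The by-phase adverse event table gives crude percentages with no phase denominator or person-time, so its three phases of unequal length cannot be compared with one another

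*SAP*

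**What the plan says.** - **The table.** SAP 7.5.1 calls for one overall summary "by treatment group and overall by analysis phase (Treatment, 1-Year Follow-Up and Continued Follow-Up"). Its rows are of the type "Number and percentage of subjects with AEs", plus a count of deaths. Section 7.5 plans no rate per unit of time.
- **The denominator.** Section 7.5 says the safety tables are for the Safety Analysis Set (SAF). The general rule in 7.1 is that "percentages by categories will be based on the number of subjects with no missing data", unless otherwise specified. Neither says whether a man who never enters a phase counts in that phase's percentage. Section 7.1 leaves table formats to separate specifications, which are not part of the document.
- **The phases (6.4).** "Treatment Phase is defined as date of first study drug dose (or randomization for AS) until either 30 days post treatment end date", or study discontinuation if earlier. "1-Year Follow-Up Phase is defined as 31 days post treatment end date until either completing 1-Year Follow-Up", again with discontinuation if earlier. "Continued Follow-Up Phase is defined as the day after completing 1-Year Follow-Up phase until study discontinuation date".
- **The end of follow-up.** Note 1 to Table 2: "Subjects will be followed every 6 months until the last subject (study-wide) has completed the 24m Visit".
- **Visits.** Section 3.2: "Subjects will be followed up every 3 months for these 2 years, after which follow-up will either be every 6 months or unscheduled".
- **The two arms.** In the 6.4 definition of treatment-emergent events, the active surveillance (AS) window is fixed at one year plus 30 days. The enzalutamide window follows the actual end of treatment.

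**The concern.** The percentage of subjects with at least one AE depends on how long they are watched as well as on how often events occur. The three phases differ in length. The last one has a length set by each man's enrolment date, and the set of men still under observation shrinks from phase to phase. Placed side by side, crude percentages can move a good deal when the AE rate has not changed at all. This affects how post-treatment safety is described. It does not touch the primary endpoint.

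**Working it through.** **Inputs.** Section 4 gives one-year accrual, a three-year study, 222 subjects and 16% loss to follow-up. Table 2 puts the 12-month visit at day 358 and the 24-month visit at day 730. The SAP states no AE percentage by phase, so the AE incidences below are assumptions.

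**1. The plan's own figure.** The SAP's 72 primary events rest on the same accrual, duration and loss. Expected events per arm are 111 × the mean, over entry times u from 0 to 1 year, of [λ/(λ+η)]·[1 − exp(−(λ+η)(3 − u))]. Here λ = 0.2310 or 0.1189, and η = −ln(0.84)/3. The two arms sum to 72.1, which agrees. Reading 16% as an annual loss gives 63.4. I therefore take 16% as cumulative over three years.

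**2. Phase lengths for a full-year completer.**
- Treatment: 365 + 30 = 395 days (358 + 30 = 388 if drug ends at the 12-month visit).
- 1-Year Follow-Up: 730 − 395 = 335 days (or 730 − 388 = 342).
- Continued Follow-Up: uniform on 0 to 365 days, mean about 183. About half the men reach a month-30 visit.

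**3. Constant first-event hazard r, no loss.** r = −ln(1 − p)/395, where p is the Treatment Phase percentage. 1-Year Follow-Up is 1 − exp(−335r). Continued Follow-Up is the mean of 1 − exp(−rd) over d from 0 to 365.

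| Treatment (assumed) | 1-Year Follow-Up | Continued Follow-Up |
|---|---|---|
| 30% | 26.1% | 14.8% |
| 50% | 44.4% | 26.2% |
| 80% | 74.5% | 48.0% |

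With 388 and 342 days, the 50% row becomes 45.7% and 26.5%.

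**4. Effect of the denominator.** Add a daily loss hazard η and put h = r + η. With the whole SAF as denominator, a phase that starts at day s and lasts L days shows exp(−ηs)·(r/h)·[1 − exp(−hL)]. At 16% over three years, the 50% row becomes 48.6%, 40.8% and 22.9%. With phase entrants as denominator, the last two are 43.4% and 25.7%. The denominator matters, but most of the last drop comes from length, so changing the denominator alone does not cure it.

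**5. Early stopping.** Take r = ln 2/388 and let 1-Year Follow-Up end at day 730.
- Stop at day 335: 365 days in each phase, 47.9% in each.
- Stop at day 180: 210 and 520 days, 31.3% and 60.5%.
- An arm with 10% early stoppers spread uniformly over the year: 48.0%, then 47.1%.
- An arm with 20%: 46.0%, then 48.5%, so the percentage rises.

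If 1-Year Follow-Up instead means one year from treatment end, it lasts 365 − 30 = 335 days, and the order still reverses for stops before day 335 − 30 = 305.

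**6. Between arms.** If the AS Treatment Phase is taken as 395 days, the same hazard gives AS 50.6%. The enzalutamide arm with 20% early stoppers shows 46.0%, a difference produced by observation time alone.

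**7. What a rate does.** In a phase of length L, expected subjects with an AE are 1 − exp(−rL), and expected time to first AE or phase end is [1 − exp(−rL)]/r. Their ratio is r in every phase: 100 × 365.25 × ln 2/395 = 64.1 per 100 patient-years. The time must stop at the first AE. Dividing by total patient-years would give 0.500/(395/365.25) = 46.2, 0.444/(335/365.25) = 48.5 and 0.262/(182.5/365.25) = 52.3 per 100, which still drifts with length.

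**The case against.** The strongest reply is that the table is a descriptive summary in an open-label exploratory study. Section 7.5.1 plans no contrast between phases, and AE listings are planned as well. Each phase is shown by arm, so AS stands beside enzalutamide and would show a similar artificial fall. This stands in part, and it is why the point carries modest weight. It does not dispose of the point. The SAP does not say the table is to be read within phase, the overall column has no comparator, and AS is an imperfect check once men stop drug early (steps 5 and 6).

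Four stronger readings are tempting and are not supported:

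- **That AE percentages fall from phase to phase by construction.** The first step is about 4 to 6 points for full-year completers and can reverse.
- **That the table will suggest recovery after stopping enzalutamide.** The SAP nowhere gives the table that purpose. The large drop also lies between two phases that are both off drug.
- **That men who never enter a later phase stay in its denominator.** The SAF is one reading of a rule that the SAP leaves open, and the table specifications may settle it.
- **That visit frequency differs throughout.** Visits are 3-monthly in both of the first two years and become 6-monthly only after month 24. The SAP gives no basis for sizing any effect of that on AE reporting.

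**Conclusion.** The point holds in a limited form. As planned, the by-phase percentages move with phase length, enrolment date and time of stopping drug as well as with the AE rate, so they cannot be compared across phases in either direction. The effect is largest for Continued Follow-Up: about 26% against 44% in the preceding phase, with no change in rate, if the Treatment figure is 50%. These figures assume a constant hazard, uniform one-year accrual as planned, and illustrative AE incidences. The 50%, 44% and 26% also assume full completion. Longer actual accrual would lengthen Continued Follow-Up and weaken the last drop. Nothing in the SAP is contradictory here. This is a cheap improvement to a descriptive table.

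**What to change.** In SAP 7.5.1, for the by-phase table:

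1. Define the percentage denominator as the subjects who enter the phase.
2. Show the number of subjects at risk and total patient-years for each phase and arm.
3. Beside the crude percentages, add subjects with an AE per 100 patient-years at risk, with time at risk in the phase ending at the subject's first AE in that phase.
4. State that comparisons are made between arms within a phase, and that crude percentages are not compared across phases.

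The dates needed are those already collected to define the phases. The cost is some SAP wording and a few columns in one table. The downside is a slightly larger table, and rates that assume a roughly constant hazard within each phase. The crude percentages stay in view beside them.

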7. Clinical labs, which will be assessed by the study's central laboratory, include serum chemistries (comprehensive metabolic panel) and hematology (CBC with differential).
8. Serum hormonal levels to be measured are testosterone, DHT, dihydroepiandrosterone, androstenedione and estradiol.
9. Serum PSA will be measured by the study's central laboratory.
10. If warranted per Investigator's clinical opinion or per standard of care.
11. [REDACTED] **CCI** [REDACTED].
12. Biopsies may be done with or without mpMRI targeting. Sites must use a consistent method (either with or without mpMRI targeting) for all of their study subjects. Any biopsy performed during the subject's study participation will be analyzed centrally (for histological reading, [REDACTED] **CCI** [REDACTED]).
13. Biopsy must be done within 6 months prior to the Screening Visit, and submitted for central analysis (histological reading, [REDACTED] **CCI** [REDACTED]). For this biopsy, a minimum of 10 cores is required.
14. Subjects who withdraw from the study prior to the 24m Visit will be asked to complete all subject reported outcomes questionnaires (BFI, SF-12, EPIC, MAX-PC) at their final study visit.
15. Only the urinary, sexual and hormonal domains will be used.
16. Adverse events (serious and non-serious) will be collected from the time the subject signs the consent form until the subject completes the study.
17. Study drug is only applicable to subjects randomized to the enzalutamide arm; subjects randomized to AS will not be dispensed any study drug.
18. Subjects will have the option of having an additional sample collected at each phlebotomy session for storage and analysis in future trials of future trials of biomarker discovery for localized prostate cancer

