## **7.10 Handling of Missing Data, Outliers, Visit Windows, and Other Information**

### **7.10.1 Missing Data**

As a general principle, no imputation of missing data will be done. Exceptions are the start and stop dates and relationship of AEs and CMs and visit windows.

All analysis will be based on available data to summarize safety and efficacy results.

However, a conservative approach to partial dates and missing adverse event relationships will be as follows:

- For survival analyses, if a subject's death month and year are provided but the day is missing, the day will be set to the first day of the month, unless other qualifying study data support survival until a later date in the same month.
- For subjects in the enzalutamide arm, adverse events with partial dates with the same month and year as the first dose date of study drug will be considered as treatment-emergent adverse events.
- For subjects in the enzalutamide arm, if an adverse event's relationship is missing, it will be assumed to be related.
- For subjects in the enzalutamide arm, if the AE or CM start day is missing, then impute the 1st of the month unless month and year are the same as the month and year of first dose of study drug, then impute AE/CM start date with the first dose date. If the start month and day are both missing, then impute 01JAN unless the year is the same as first dose date, then impute AE/CM start date with the first dose date. If the entire start date is missing, then no imputation will be performed, but the AE will be considered treatment-emergent.
- For subjects on active surveillance, if the AE or CM start day is missing, then impute the 1st of the month unless month and year are the same as the month and year of randomization, then impute AE/CM start date with the randomization date. If the start month and day are both missing, then impute 01JAN unless the year is the same as randomization date, then impute AE/CM start date with the randomization date. If the entire start date is missing, then no imputation will be performed, but AE will be considered to have occurred on or after randomization date.

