- For subjects in the enzalutamide arm, if the adverse event or concomitant medication end day is missing, then impute the last day of the month unless month and year are the same as month/year of last dose of study drug, then impute last dose date. If the end month and day are both missing, then impute 31DEC unless year is the same as first dose date, then impute last dose date. If the entire end date is missing, then no imputation will be performed and the event will be considered "ongoing."
- For subjects on active surveillance, if the adverse event or concomitant medication end day is missing, then impute the last day of the month unless month and year are the same as month/year of last day of 1 year of active surveillance, then impute last date on active surveillance. If the end month and day are both missing, then impute 31DEC unless year is the same as randomization date, then impute last date on active surveillance. If the entire end date is missing, then no imputation will be performed and the event will be considered "ongoing."

All AE and concomitant medication imputation of missing dates and relationship will be

considered for tabular summaries but not for data listings. Data listings will display missing values. Subjects who do not receive the study drug to which they have been randomized will be analyzed as treated.

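### Sections 7.5.1 and 7.10.1 give different rules for a missing AE relationship; read literally, 7.5.1 would count blanks in the untreated AS arm as drug-related

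*SAP*

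**What the plan says.** SAP section 7.5.1 (Adverse Events) plans an overall AE summary with columns per treatment group and in total. One row is "Number and percentage of subjects with causally drug-related AEs", and there is a matching row for serious events. Tables by system organ class and preferred term follow for the same categories, and then tables by relationship and by maximum grade. Directly after these comes the missing-value rule: "For subjects with missing relationship, the most conservative (related) will be assumed for table summaries".

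SAP section 7.10.1 (Missing Data) starts from a default of no imputation and lists AE relationship among the exceptions. It introduces its detailed rules as "a conservative approach to partial dates and missing adverse event relationships will be as follows". The relationship rule in that list is "For subjects in the enzalutamide arm, if an adverse event's relationship is missing, it will be assumed to be related". The AS arm has its own entries, for example the one that begins "For subjects on active surveillance, if the AE or CM start day is missing", but they cover dates only. The section closes with a sentence that begins "All AE and concomitant medication imputation of missing dates and relationship will be" and applies these imputations to tables and not to listings.

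Two further statements fix who is in the tables. Section 7.5 opens with "The following summary tables and listings will be displayed for the SAF", and section 5.3 equates that set with the full analysis set, so AS men are included. A footnote to Table 2 states that "subjects randomized to AS will not be dispensed any study drug".

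**The concern.** For an AS event whose relationship field is empty, the two sections give different answers. Section 7.5.1 makes it related; section 7.10.1 leaves it missing. Both govern the summary tables, and the SAP has neither a cross-reference between them nor a statement of which prevails.

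The result under 7.5.1 would be wrong on its face, because a man who was dispensed no study drug would be counted with a drug-related event. Assuming the worst is cautious in the enzalutamide arm, where it cannot hide toxicity. In the comparator arm it works the other way: it raises the AS count and makes any excess on enzalutamide look smaller. The total column would carry the same error.

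**Working it through.** The plan states no figure to reproduce, so the check is a comparison of the two rules, followed by bounds on the effect.

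**Rules side by side, for an AE with blank relationship in the summary tables**

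| | Section 7.5.1 | Section 7.10.1 |
|---|---|---|
| Arm named | none | enzalutamide only |
| Enzalutamide event | related | related |
| AS event | related (literal reading) | no rule given, so the default of no imputation applies |
| Output affected | table summaries | tables, not listings |

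The rules agree for enzalutamide and differ only for AS.

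**Does the difference reach a table?** Yes.
1. The AE tables are run on the safety analysis set (7.5).
2. That set is stated to equal the full analysis set, which is everyone randomized (5.1, 5.3). Section 8 notes one exception, men assigned to enzalutamide who stop before a first dose. It does not remove AS men.
3. The overall summary and the organ-class tables are shown per arm and in total, so there is an AS column under the drug-related headings. The sentence on by-relationship tables does not state its columns.
4. Section 7.5.1 also shows a repeated event once, at its highest grade and strongest relationship. Under the literal reading, one blank among several reports of an event would be enough to display it as related.

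**How large could it be?** Let N be the number of AS men, p the proportion with at least one AE, and b the proportion of those with at least one blank relationship. The number wrongly shown with a drug-related AE is at most N × p × b.
- N = 222 / 2 = 111 under 1:1 allocation (sections 3.2 and 3.3).
- p is not given in the SAP.
- b is not given, and the SAP does not say whether the field is left blank, set to not related, or set to not applicable for AS men.

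At b = 0 the count is 0. At b = 1 it is 111 × p, that is, every AS man with an AE. The documents do not place the trial between these limits.

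**The case against.** The strongest reply is that 7.10.1 already settles the matter. It presents itself as the detailed statement of the conservative approach, it applies to the same tables, and it writes separate AS rules for dates while leaving AS out of the relationship rule. That omission looks deliberate, and 7.5.1 can be read as shorthand for it. On this reading AS relationships are never imputed. This is a reasonable reading and probably the intended one, but nothing in the SAP makes it binding. Section 7.5.1 is the section on the AE tables, its sentence sits immediately after the by-relationship tables, and a programmer could follow it as it stands.

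The reply does stand against stronger readings. A reader might infer that the plan requires imputation in both arms; 7.5.1 does not say so, and its reach into AS comes only from its silence on arm. A reader might also infer that a blank is the expected entry for an AS man because he receives no drug. The Table 2 footnote says only that none is dispensed and is silent on how the form is completed. It follows that a count such as 56 to 89 men (0.50 × 111 to 0.80 × 111, with 50% to 80% an assumed AE rate) is not an estimate: it also sets b to 1, and the documents support no value of b.

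It is also fair that these rows are descriptive, that 7.5.1 plans no between-arm test of them, and that section 1 schedules a review of data and tables before hard lock, where a large drug-related count in an untreated arm would be noticed. A handful of such events might not be.

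**Conclusion.** The inconsistency is real and minor. The two sections differ in scope, and the unrestricted one, followed literally, would put drug-related events into the column of an arm that receives no drug. The direction is clear: the AS column is inflated and any enzalutamide excess in the drug-related AE and SAE rows is narrowed. The size is not derivable and runs from 0 to every AS man with an AE, depending on how relationship is recorded for AS men.

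The documents do not support saying that the arm comparison would reverse, or that the plan as a whole prescribes the error. The primary analysis is unaffected. The conclusion rests on two things: AS men being in the safety set, which the SAP states, and at least some AS events having a blank relationship, which it neither states nor excludes.

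**What to change.** In 7.5.1, replace the sentence with: 'For subjects in the enzalutamide arm, a missing relationship is assumed related (see 7.10.1).' Add that relationship to study drug is not imputed for AS subjects and is shown as not applicable. It would help to state in the same place how the field is completed for AS men.

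Whether to keep a total column for the drug-related rows is a presentation choice and is not needed to resolve the conflict.

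The cost is one or two sentences and a small edit to the table shells. Section 1 allows version-controlled revisions until database hard lock; after that, the rule actually applied should be stated in the study report.
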